9.6 Treatment stopping rules

The trial may be prematurely discontinued by the Sponsor, Chief Investigator or Regulatory Authority on the basis of new safety information or for other reasons given by the Data Monitoring & Ethics Committee/ Trial Steering Committee regulatory authority or ethics committee concerned.

The trial may also be prematurely discontinued due to lack of recruitment or upon advice from a Trial Steering Committee, who will advise on whether to continue or discontinue the study and make a recommendation to the sponsor. If the trial is prematurely discontinued, active participants will be informed and no further participant

data will be collected. The Competent Authority and Research Ethics Committee will be informed and no further participant data will be collected.

Treatment stopping rules for individual patients will include voluntary discontinuation by the patient, a change in inclusion or exclusion criteria of the clinical trial or the development of a SUSAR/SAE/SAR.

10 Statistics

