4.1.3 Primary endpoint

- Adverse events (AEs), Serious Adverse Events (SAEs), Adverse Reactions (ARs) and Serious Adverse Reactions (SARs) at each visit after screening over a 12-month follow-up period.

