4.2 Trial design

This is a prospective phase 1, non-randomised, open label, single-centre, proof-of-concept study. Each study participant will receive three intradermal injections of ex vivo transduced autologous fibroblasts expressing codon-optimised COL7A1 as the IMP on Day 0 only. Each injection of the IMP containing $0.8\text{--}1.2 \times 10^6$ cells suspended in 0.25ml of 0.9% saline, will be administered intradermally into 1cm² area of intact skin (x3). Participants will be followed up with study interventions for a 12-month period at various time points as outlined in the trial timeline (**Figure 16**). All follow-ups, where possible, will be co-ordinated to try to coincide with the individuals' routine clinic reviews.

Each subject will undergo an initial screening including a physical examination and assessment of disease severity. Blood analyses and skin biopsies will be performed at various time points as per the monitoring schedule (**Table 2 and Figure 16**). The second participant will be treated only if there is no safety concern 4 weeks after the first participant's IMP injections. All patients with RDEB are followed up on a lifelong basis, and we will therefore be able to capture any long-term possible adverse effects related to the IMP.

LENTICOL-F Version 4.0, 01/MAR/2016

EudraCT Number: 2014-004884-19

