6.5 Withdrawal of subjects

Participants have the right to withdraw from the study at any time for any reason. The investigator also has the right to withdraw patients from the study drug in the event of inter-current illness, AEs, SAEs, SUSARs, protocol violations, cure, administrative reasons or other reasons. It is understood by all concerned that an excessive rate of withdrawals can render the study un-interpretable, therefore unnecessary withdrawal of patients should be avoided. Should a patient decide to withdraw from the study, all efforts will be made to report the reason for withdrawal as thoroughly as possible.

Should a participant withdraw from the study after the injection of the IMP, efforts will be made to continue to obtain follow-up data, with the permission of the participant. If a participant withdraw before the IMP injection, the participant will be replaced.

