6.6 Expected duration of trial

The planned duration of the study will be 32 months. Each trial participant will be followed up for 12 months after the last intradermal injections of the IMP: gene-modified autologous fibroblasts. We may recruit and produce the IMP for more than one participant at a time, though only administer the IMP with minimal intervals between individuals.

Each participant will have a screening visit up to 4 months prior to Day (D) 0 when the IMP will be administered. There will be 7 scheduled follow-up visits over 12 months from Day 0. Safety and efficacy will be assessed initially using the first 12 month data. Participants will then be reviewed every 4 months for the second year and then every 6 months for the third year by the consultant dermatologist responsible for their clinical care ([name] or [name] who are the tenured senior clinical investigators for this trial) or an experienced EB specialist nurse. If a participant does not wish to attend for a 4-month or 6-month hospital visit, we will offer them the option of a telephone call to enquire about adverse events which will be recorded in the eCRF. All trial participants also have direct access to the EB specialist nurses should they develop any untoward symptoms requiring urgent clinical review, or wish to discuss any additional aspects of the clinical trial, in the interim between these time points. All adult subjects (aged ≥ 17 years) within the EB service are regularly seen at St John's Institute of Dermatology at GSTT. [name] and [name] provide consultant care dedicated to this service.

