6.7 End of trial definition

The point will be defined as the final study participant's last scheduled follow-up visit according to the protocol, which will be the 12 month follow-up visit after the intradermal injections of the IMP of the last subject entering the trial.

7 Trial Procedures

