7.2 Long-term follow-up

Patients with RDEB are regularly reviewed, often for life, by the consultant Dermatologists in the multi-disciplinary setting at the regular EB clinics at GSTT, providing opportunities for detection of late adverse events. Once these studies are officially closed we will continue to report serious events related to the IMP (SARs and SUSARs) to the MHRA and London – West London & Gene Therapy Advisory Committee (GTAC) in the same way as during the study.

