7.4. Procedures by visit

Visit number	V1A	V1B	V2	V3	V4	V5	V6	V7	V8	V9
Timeline of each visit relative to the day of gene-modified fibroblast injections (D0)	Up to 6M prior to D0	At least 6W prior to D0	D0	W1 (±3D)	W2 (±3D)	W4 (±14D)	M3 (±1M)	M6 (±1M)	M9 (±1M)	M12 (±1M)
Approximate duration of each visit (hours)	2	2	1.5	1.5	2	1.5	2	1.5	1.5	2
Informed consent	X									
Inclusion / exclusion	X	X								
Demographics	X									
Medical history	X									
Vital signs	X	X	X	X	X	X	X	X	X	X
Physical examination	X	X	X	X	X	X	X	X	X	X
Serum pregnancy test for female participants with child-bearing potential (if serum is not obtainable, urine pregnancy test may be used)	X	X	X							
^a BEBS Score	X				X		X			X

Visit number		V1A	V1B	V2	V3	V4	V5	V6	V7	V8	V9
Timeline of each visit relative to the day of gene-modified fibroblast injections (D0)		Up to 6M prior to D0	At least 6W prior to D0	D0	W1 (±3D)	W2 (±3D)	W4 (±14D)	M3 (±1M)	M6 (±1M)	M9 (±1M)	M12 (±1M)
^b Clinical photography		X	X	X	X	X	X	X	X	X	X
Blood samples	^c Basic bloods	X		X		X	X	X	X		X
	^d Virology	X	X								
	C7 ELISA & IIF	X				X	X	X	X		X
	ELISPOT			X			X		X		X
	^e RCL	X				X	X	X			X
Skin biopsies	C7 IF microscopy & TEM		X			X		X			X
	^f qPCR		X			X		X			X
	^g Integration site analysis		X			X		X			X
Skin procurement (1x6mm)	Tissue culture for IMP production		X								
^h Intradermal injections of IMP				X							
Adverse event(s) assessment			X	X	X	X	X	X	X	X	X
Concomitant medications assessment			X	X	X	X	X	X	X	X	X

Table 2: LENTICOL-F trial flowchart with details of interventions at each visit. Abbreviations: V=Visit; D=Day; W=Week; M=Month. Consent will be obtained at each visit. On Day 0, your vital signs will be monitored every 15mins for 30mins after the gene-modified fibroblast injections. There will be one-off readings of the vital signs on the rest of the other visits during the study. Historical samples/ results may be used for C7 ELISA & IIF, ELISPOT, C7 IF microscopy & TEM. Historical virology results performed within the last 3 months may be used. **NB: If W2 and M3 skin biopsy results are negative then M12 biopsy may not be performed.**

^aBirmingham Epidermolysis Bullosa Severity Score;

^bClinical photography of potential injection sites over an area of the intact skin will be taken at screening on visit 1, post-IMP injections on visit 2 and at each visit thereafter;

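### Protocol 9.6 ends participant data collection on an early stop, which truncates the 12-month primary safety endpoint for participants already injected

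*Protocol*

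**What the plan says.** Protocol 9.6 allows the trial to be discontinued early for new safety information, for other reasons given by the oversight bodies, or for lack of recruitment. It then says, once in connection with informing participants and once in connection with informing the authorities, that data collection ends: "The Competent Authority and Research Ethics Committee will be informed and no further participant data will be collected". Neither statement separates participants already injected from those still in screening.

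The other passages that bear on this are:

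- **Primary endpoint (Protocol 4.1.3, SAP 1.12.1).** Adverse events, serious adverse events and the corresponding reactions, "at each visit after screening over a 12-month follow-up period".
- **Treatment (Protocol 4.2).** Three injections on Day 0 and none later. "The second participant will be treated only if there is no safety concern 4 weeks after the first" participant's injections.
- **Individual withdrawal (Protocol 6.5).** "Should a participant withdraw from the study after the injection of the IMP, efforts will be made to continue to obtain follow-up data", subject to permission.
- **Planned follow-up (Protocol 6.6).** Twelve months per participant, then review every 4 months in year 2 and every 6 months in year 3. For those who prefer not to attend, "we will offer them the option of a telephone call to enquire about adverse events which will be recorded in the eCRF".
- **End of trial (Protocol 6.7).** The last scheduled visit of the final participant, "which will be the 12 month follow-up visit after the intradermal injections of the IMP of the last subject entering the trial". Protocol 10.2 and SAP 2.8 time the final analysis in the same way.
- **After closure (Protocol 7.2, repeated in SAP 1.8).** "Once these studies are officially closed we will continue to report serious events related to the IMP (SARs and SUSARs") to the regulator and the ethics committee.

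SAP Table 6 summarises safety as numbers of events and numbers of patients with at least one event. It has no follow-up time.

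**The concern.** With a single treatment day, an early stop leaves an injected participant no study treatment to discontinue. What 9.6 ends for that person is observation. The participants affected are those whose safety the primary endpoint is meant to describe, and one of the triggers is a safety signal.

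The rule is also out of step with 6.5. A participant who chooses to leave after injection may still be followed for data, while a willing participant in a stopped trial is not.

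The loss would be structured eCRF capture of non-serious events and reactions and of unrelated serious events, together with the remaining scheduled antibody and T-cell tests. Later blood samples archived for replication-competent lentivirus, and later biopsies archived for integration-site analysis, would not be taken under the protocol either. All participants stay in the analysis (Protocol 10.2, SAP 2.4). Table 6 would therefore count someone cut off at week 4 without an event in the same way as someone event-free for 12 months.

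**Working it through.** **The plan's own precision figure.** Protocol 10.1 and SAP 1.14 give an exact 95% interval of 0% to 31% for no reactions in 10 subjects. The upper limit is 1 − 0.025^(1/n). For n = 10 it is 30.85%, so the figure reproduces. If a 12-month statement had to rest only on participants who reached month 12 before a stop, the zero-event limit would be 52.2% with 5 such participants and 70.8% with 3. With none there is no 12-month estimate. This is an illustration: partly followed participants still contribute information, and continued follow-up cannot replace people never injected.

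**Loss per injected participant.** Post-injection assessments in Protocol Table 2 are:

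- adverse event visits at W1, W2, W4, M3, M6, M9 and M12 (7)
- ELISA/IIF at W2, W4, M3, M6 and M12 (5)
- ELISPOT at W4, M6 and M12 (3)
- archived lentivirus bloods at W2, W4, M3 and M12 (4; Protocol 9.1 omits W4, which does not change the number lost below)
- biopsies at W2, M3 and M12 (3, with M12 conditional on earlier results)

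Uncollected time = 1 − d/365, with nominal d = 28, 91.25, 182.5 and 273.75 days. The ranges use the visit windows: 14–42 days for W4, then 2–4, 5–7 and 8–10 months out of 12.

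| Stop just after | AE visits lost | ELISA/IIF lost | ELISPOT lost | Lentivirus bloods lost | Biopsies lost (up to) | Time lost, nominal (range) |
|---|---|---|---|---|---|---|
| W4 | 4/7 | 3/5 | 2/3 | 2/4 | 2/3 | 92.3% (88.5–96.2%) |
| M3 | 3/7 | 2/5 | 2/3 | 1/4 | 1/3 | 75.0% (66.7–83.3%) |
| M6 | 2/7 | 1/5 | 1/3 | 1/4 | 1/3 | 50.0% (41.7–58.3%) |
| M9 | 1/7 | 1/5 | 1/3 | 1/4 | 1/3 | 25.0% (16.7–33.3%) |

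**Loss at trial level.** The documents define two checkpoints. Neither is stated to be a stopping point, so these figures only show scale.

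1. *Four-week review of the first participant.* A stop here leaves the only treated participant with 28/365 = 7.7% of the planned follow-up.
2. *Interim analysis, when all have completed the month-6 visit.* The least loss occurs if everyone but the last participant has finished. The most occurs if all are at month 6 except the first, who is at least 28 days (0.92 months) ahead and so loses 5.08 months.
   - Nominal days, n = 5: from 6/60 = 10.0% to (4×6 + 5.08)/60 = 48.5%.
   - Nominal days, n = 10: from 6/120 = 5.0% to (9×6 + 5.08)/120 = 49.2%.
   - With the ±1-month window on that visit, n = 5: from 5/60 = 8.3% to (4×7 + 6.08)/60 = 56.8%.
   - With the same window, n = 10: from 5/120 = 4.2% to (9×7 + 6.08)/120 = 57.6%.

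A stop before the first participant's month-12 visit leaves nobody with the full endpoint.

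**Does another passage repair the rule?** Protocol 7.2 and SAP 1.8 keep only related serious events. Protocol 9.4 puts adverse events in the patient notes, which are not the trial database. Protocol 6.5 concerns individual withdrawal. Protocol 6.7, 10.2 and SAP 2.8 have no early-termination version. None of these restores the 12-month endpoint.

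**The case against.** Much can fairly be said on the other side.

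- **A reader might infer that 9.6 flatly contradicts 6.6.** The documents do not go that far. 6.6 sets out the planned course and is silent on early termination, and a stopping clause naturally departs from a planned schedule. The two are out of step and need reconciling.
- **A reader might infer that safety follow-up of injected participants would cease.** It would not. Related serious events continue to be reported, and 7.2 can be read as a specific provision standing beside 9.6, so the tension between them reaches only those events. Patients with this disease are reviewed by the clinical service, often for life. The year 2–3 reviews belong to the treating team, so only their recording as trial data would end.
- **A reader might infer that the archived safety samples become useless.** Samples already stored remain, and 9.6 does not bar sampling indicated in clinical care. Only the later scheduled samples are lost.
- **A reader might infer that the truncation would be concealed.** It would show in the SAP 2.1 flow chart, in Table 3, and in the per-patient listings read with the treatment dates in Table 5. It would not show in Table 6, which gives counts rather than rates.
- **Unseen documents may help.** The SAP refers to a data monitoring committee charter, and the consent text is not available. Either might cover follow-up after a stop.

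These points limit the consequence. They do not alter the unqualified wording of 9.6 or bring back the primary endpoint data.

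**Conclusion.** The concern stands and should be fixed. Protocol 9.6 is a stated rule, not an omission. If followed, it removes between about a quarter (stop at M9) and about nine-tenths (stop at W4) of an injected participant's primary safety follow-up.

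The residual loss is moderate, because related serious events and clinical care continue. It arises only if the trial is discontinued early, and the documents give no basis for putting a probability on that. The per-participant percentages rest on nominal visit days and a 365-day year. The interim range, about 4% to 58% once the visit window is allowed for, assumes a stop at a point the documents do not name as one.

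**What to change.** Reconcile Protocol 9.6 with 6.5, 6.6 and 7.2/SAP 1.8:

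1. Replace both statements in 9.6 so that, with consent, adverse event, serious adverse event and reaction data on participants already injected continue to be recorded in the eCRF at the existing visits up to month 12.
2. Add one SAP sentence saying that these data enter Tables 6 and 7, and cross-refer from 6.5 and 6.7.
3. Have the sponsor state which scheduled blood tests and biopsies, if any, continue after a stop.
4. Add follow-up time per treated participant (in Table 5 or 7, for example) and total patient-months beneath Table 6.

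The drafting is small and needs no new type of visit. The real cost is that visits, database and monitoring stay open for up to about 13 months after a stop (12 months plus the +1-month window on the last visit). These have to be staffed and funded, and participants are asked to keep reporting in a stopped trial. The change concerns data recording only. It proposes no treatment, stopping or other clinical rule.

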10.1 Sample size

The aim of this phase 1 trial will be to recruit approximately 5–10 patients from GSTT EB clinical database. As described previously this is a rare disease with an incidence of 1 in 17,000 live births. As per our statistician's advice, even if no subjects experienced adverse reactions (i.e. 0% AR), a sample size of 10 would give a 95% confidence interval of 0% to 31% (exact CI from Stata®). A sample of 10 could still potentially provide reassurance that no more than 3 in 10 subjects should experience a given side-effect.

10.2 Analysis

All study participants will be included in all analyses unless they have withdrawn consent. For subjects who drop-out rather than withdrawn consent, a request will be made to use data collected prior to drop-out. Descriptive statistics such as means, standard deviations (SDs), minimum and maximum frequencies and proportions, as appropriate will be presented. No hypothesis tests will be performed. When all participants complete Visit 7 (Month 6), an interim analysis of the collected data will be performed and the results will be published in a peer-reviewed journal and there will be another analysis at the end of the trial (12 months after the last participant's cell injections).

11 Trial Steering Committee

The Trial Steering Committee (TSC) consists of a panel of scientists specialised in the field of EB who will provide constructive criticism and suggestions to improve both the clinical trial implementation and data evaluation.

The Steering Committee shall be responsible for:

- Providing feedback and routine assessment of progress of LENTICOL-F as a whole.
- Ensuring all the work meets the functional requirements and is in accordance with the project deliverables and where necessary GCP and/or GMP compliant.
- Maintaining a complete overview of the scientific and process development progress of the project in relation to external progress in the various fields related to the project.
- Collecting and reviewing aggregate safety data, with the authority to recommend premature termination of the trial if felt necessary.

12 Direct Access to Source Data and Documents

The Investigator(s) will permit trial-related monitoring, audits, IREC review, and

regulatory inspections by providing the Sponsors, Regulators and REC direct access to source data and other documents (e.g. patients' case sheets, blood test reports, X-ray reports, histology reports etc.). The Investigators will also permit authorised inspectors to inspect all facilities and records relating to the study and aid the inspector(s) to perform the audit in a timely manner.

13 Ethics & Regulatory Approvals

The trial will be conducted in compliance with the principles of the Declaration of Helsinki (1996), the principles of GCP and in accordance with all applicable regulatory requirements including but not limited to the Research Governance Framework and the Medicines for Human Use (Clinical Trial) Regulations 2004, as amended in 2006 and any subsequent amendments.

Prior to the initiation of the trial, the Investigator will submit the protocol, subject information sheet, subject consent form, letter to the GP and any other related documents to the appropriate Independent Research Ethics Committee (IREC), London – West London & GTAC, and to the MHRA for Clinical Trial Authorisation. The Chief Investigator will submit a final report at conclusion of the trial to the KHP-CTO (on behalf of the Sponsor), the REC and the MHRA within the timelines defined in the Regulations.

14 Quality Assurance

Monitoring of this trial will be to ensure compliance with Good Clinical Practice and scientific integrity will be managed and oversight retained by the KHP-CTO Quality Team. The relevant regulatory authorities also have the right to conduct an inspection of the study, that the study was, in fact, performed at stated sites and that the data reported to the authorities reflects the data in the records of the Investigator. The authorities also inspect such studies to verify that the studies were conducted in accordance with government regulations relating to the IEC and informed consent. It is

the joint responsibility of the sponsor, co-sponsor and the Investigators to ensure that the study has been conducted in line with all relevant regulations and KCL standard operating procedures.

15 Data Handling

The Chief Investigator will act as custodian for the trial data. The following guidelines will be strictly adhered to:

- Patient data will be anonymised and coded.
- This clinical trial will use the Biomedical Research Centre's (BRCs) industry-standard secure database called MedSciNet. All access to the MedSciNet data system is controlled using a Username/Password login. Passwords are encrypted before storing to database, using SHA-1 hash (MS .NET SHA1CryptoServiceProvider). These are created and controlled by Administrative users of the system as identified by the Chief Investigator. The data is stored in the BRC eCRF servers which are located in Holland and meet or exceed all MHRA requirements for CTIMP data storage. Only the server administrator has access to this server and the core database, via remote connection. The back up process is twofold: every 24hrs the database is backed-up to the server and every 7 days the entire server is backed up to an archival tape system.
- The final database will be stored in a read-only format for 5 years before being archived onto the server for a further 2 years. At this point the archived version will be compressed and will remain in the server and a copy will be sent to the CI. The documents that relate to ATIMP traceability will be retained for a minimum of 30 years after the expiry date of the IMP. In order to meet regulatory requirement, at GSTT, hard copies of Care Report Forms will be kept in a locked filing cabinet in a locked office with the Trial Site File as per King's Health Partners-Clinical Trial Office (KHP-CTO) Standard Operating Procedure (SOP) – The Creation and Maintenance of Trial Master Files and Essential Documentation (available on the KHP-CTO website). The Trial Master File will be archived as per current KHP-CTO SOPs. All trial data will be stored in line with the Medicines for Human Use (Clinical

Trials) Amended Regulations 2006 and the Data Protection Act and archived in line with the Medicines for Human Use (Clinical Trials) Amended Regulations 2006 as defined in the KHP-CTO Archiving SOP.

16 Data Management

Electronic Case Report Forms (eCRFs) will be used to capture the data of each subject enrolled in the study. These will be standardised and protocol specific and create a time stamped electronic record of any amendments or additions to the document. eCRF pages will be monitored on an on-going basis by the study monitors.

17 Publication Policy

It is intended that the results of the study will be reported and disseminated through posters and oral presentations at international conferences, scientific meetings and in high impact peer-reviewed scientific journals. Publicity will be performed through press releases at the local, national and international levels. Press releases will be co-ordinated through King's College London, Sohna Research Fund (SRF) and DEBRA UK. SRF and DEBRA UK will also inform patients and potential participants through their website and newsletters.

18 Insurance / Indemnity

